9.4.1 Participant Disposition and Protocol Deviations

All participants who provide informed consent (ie, the Entered Population) will be accounted for in this study. Participant enrollment and disposition will be summarized by treatment group and for all participants and will include: the number of participants entered, screen failed, enrolled, randomized (overall and by randomization strata), and dosed with the IP; the total number of participants who complete the study; and the number of participants who discontinue from the study, along with the reason for discontinuation.

The number and percentage (%) of participants included in each analysis population will also be presented.

Participants who had protocol deviations by severity classification and deviation type by treatment group and for all participants based on the Randomized Population will be listed and summarized using frequency counts and percentages. If applicable, the protocol deviation listing will flag participants whose study participation is impacted by the global pandemic COVID-19 and will include details of the impact.

9.4.2 Demographics, Other Baseline Characteristics, and Medical History

All demographic and baseline data recorded prior to dosing will be summarized using descriptive statistics or frequency counts and percentages, as appropriate, by treatment group and for all participants in the Randomized Population and the PK Population. Individual participant demographics and baseline characteristics (results from urine drug abuse screening, alcohol breath test, COVID-19 test (if performed), viral serology, β -D glucan test, QuantiFERON-TB Gold in Tube test, pregnancy, and FSH tests) will also be presented in listings.

Medical history will be coded using the most current version of Medical Dictionary for Regulatory Activities (MedDRA) dictionary, and the data will be listed and summarized using frequency counts and percentages by system organ class (SOC) and preferred term (PT) by treatment group and for all participants in the Safety Population.

9.4.3 Prior and Concomitant Medications/Therapies

Prior and concomitant medications will be coded using the latest version of the WHO Drug Global Dictionary. Prior medications are those medications that are stopped prior to IP administration. Concomitant medications are medications that are taken at least once after IP administration. Medications stopping on the same day as IP administration will be considered as concomitant medications.

Prior and concomitant medications will be listed and summarized separately using frequency counts and percentages by Anatomical Therapeutic Chemical system (Level 2) and drug PT by treatment group and for all participants in the Safety Population.

9.4.4 Efficacy Analyses

Not applicable.

9.4.5 Pharmacokinetic Analyses

Serum golimumab concentrations will be listed for all participants in the Safety Population. Summaries of serum golimumab concentrations, PK parameters, and PK similarity assessment will be based on the PK Population.

Serum golimumab concentrations will be listed and summarized using descriptive statistics by treatment group and nominal PK sampling time point. All serum golimumab concentrations that are below the limit of quantification will be labeled as such in the concentration data listings. Individual and arithmetic mean (per treatment) concentration-time profiles will also be presented graphically.

Pharmacokinetic parameters of serum golimumab will be listed and summarized by treatment group using descriptive statistics. The PK parameters will also be adjusted for protein content and will be listed and summarized (details are provided in the SAP).

In addition, PK parameters will also be summarized by treatment and randomization strata. A subgroup analysis of PK parameters by gender and Japanese, non-Japanese ≤80 kg, and non-Japanese >80 kg will also be performed.

9.4.6 Statistical Analysis for PK Similarity

The primary PK parameters for the demonstration of PK similarity between AVT05 and the Simponi reference products will be C_{max} and $AUC_{0\text{-inf}}$. The statistical analysis will be performed using an ANCOVA model on the logarithmic scale (ie, using natural log-transformed values of C_{max} and $AUC_{0\text{-inf}}$) including treatment group as fixed effect and with gender as factor and body weight at baseline as continuous covariate.

Point estimates (geometric means and GMRs) will be calculated by back transforming the LS means of the natural log-transformed values of C_{max} and AUC_{0-inf} and the difference in the LS

means. The PK similarity of AVT05 versus US-licensed Simponi, AVT05 versus EU-approved Simponi, and EU-approved Simponi versus US-licensed Simponi will be demonstrated if, for each pairwise comparison, the 90% CIs for the GMRs of the primary endpoints are entirely contained within the equivalence margin of 80% to 125% (when the ratio is expressed as a percentage). Other exploratory analyses of PK similarity by subgroups based on the randomization strata, ADA status, and NAb status may be performed if appropriate.

Differences in drug protein concentration have been identified between AVT05 (101.0 mg/mL), US-licensed Simponi (94.7 mg/mL), and EU-approved Simponi (91.4 mg/mL). Therefore, the PK similarity analysis using PK parameters adjusted by protein content will be performed as a sensitivity analysis.. Further details will be provided in the SAP.

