8.9 Inflammatory Cytokine Pharmacodynamic Assessments

For the ex-vivo pharmacodynamic assessments, venous blood samples (4 mL) were collected in lithium-heparin tubes from 45 participants (15 per group) for the measurement of IL-8 levels using an ex-vivo TNF-α stimulation assay at the time points specified in Table 2.

NOTE: As of Protocol Version 4.0, the analysis of the samples collected for the ex-vivo pharmacodynamic substudy will not be performed. The collected samples will be destroyed.

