9.2 Sample Size Determination

The primary PK endpoints for this PK study are C_{max} and AUC_{0-inf}. Sample size calculations were performed using SAS Version 9.4, and were based on PK parameter summary data from Ling and Lyn (2010). Based on this study, the inter-participant coefficient of variation (CV%) is assumed to be 35.0% for AUC_{0-inf} and 37.7% for C_{max}.

The assessment of PK similarity will be based on the 90% confidence interval (CI) for the geometric mean ratio (GMR) between 3 treatment groups will be calculated for all 3 pairwise comparisons (AVT05 to US-licensed Simponi, AVT05 to EU-approved Simponi, and EU-approved Simponi to US-licensed Simponi) for both primary endpoints AUC $_{0-inf}$ and C_{max} . The PK similarity will be demonstrated if the 90% CIs of the GMR for both AUC $_{0-inf}$ and C_{max} lie entirely within the prespecified margins of 80% and 125% (when the ratio is expressed as a percentage) in all pairwise treatment comparisons.

Assuming a true GMR of 95%, 101 evaluable participants per treatment group will provide a power of 95.5% for each individual comparison of C_{max} and a power of 97.4% for each individual comparison of AUC_{0-inf}. Considering a non-evaluable rate of 10%, the total sample size of 336 participants (112 per treatment group) will provide an overall study power of 80.5%.

Of the 336 participants, at least 10% (33 participants, 11 per group) participants of Japanese origin are planned to be enrolled.

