9.4 Statistical Analyses

The following sections describe the statistical analysis as it is foreseen when the study is being planned. A detailed Statistical Analysis Plan (SAP) will be developed and finalized before database lock and will describe the participant analysis populations to be included in the analyses, and procedures for accounting for missing, unused, and spurious data. The SAP will also provide the format of listings, tables, and figures to be provided for completion of the Clinical Study Report (CSR). Any deviations from the SAP will be presented in the final CSR. This section is a summary of the planned statistical analyses of the primary and secondary endpoints.

All statistical analyses, summaries, and listings will be performed using SAS software (Version 9.4 or higher) (SAS Institute, Inc., Cary, North Carolina, USA).

In general, data will be presented by treatment group. Data for all study participants combined will also be presented when appropriate. Individual participant data will be presented in listings by randomization strata.

The following descriptive statistics will be used as applicable to summarize the study data unless otherwise specified:

- Continuous variables: sample size (N), number of non-missing counts (n), mean, SD, median, minimum (min), and maximum (max). The CV%, geometric mean, and geometric CV% will be presented for PK parameters, where applicable.
- Categorical variables: frequency counts and percentages.

Baseline will be defined as the last available, valid, non-missing assessment (scheduled or unscheduled) prior to dosing. Only data from protocol-scheduled visits/time points will be included in the summary tables and figures. All data, including those from unscheduled visits/time points will be included in the listings.

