The PI/institution should maintain adequate and accurate source documents and study records that include all pertinent observations on each of the study site's participants. Source data should be attributable, legible, contemporaneous, original, accurate, and complete. Changes to source data should be traceable, should not obscure the original entry, and should be explained if necessary (eg, via an audit trail).

- Source documents provide evidence for the existence of the participant and substantiate the integrity of the data collected. Source documents are filed at the PI's study site.
- Data entered in the eCRF that are transcribed from source documents must be consistent with the source documents or the discrepancies must be explained. The PI may need to request previous medical records or transfer records, depending on the study. Also, current medical records must be available. Definition of what constitutes source data can be found in the eCRF completion guidelines.

Management of Protocol Amendments and Protocol Deviations

Protocol Amendments:

No changes (amendments) to the protocol may be implemented without prior approval from the Sponsor and the appropriate IRB/IEC, except where necessary to eliminate an immediate hazard to participants, or when the change involves only logistical or administrative aspects of the study. If a protocol amendment requires changes to the ICF, the revised ICF must be approved by the IRB/IEC.

Protocol Deviations:

A deviation from the protocol is an unintended or unanticipated departure from the procedures or processes that were approved by the Sponsor and the IRB/IEC and agreed to by the PI. Protocol deviations will be classified by severity ratings of critical, major, or minor, as determined by clinical staff:

- A minor protocol deviation is a deviation from accepted procedures that will not adversely affect participants or data integrity, but should be dealt with appropriately.
- A major protocol deviation is a deviation from Protocol-related procedures that could affect integrity of the data or adversely affect participants. Such deviations require timely action.
- A critical protocol deviation is deviation from Protocol-related procedures that could affect integrity of the data or adversely affect participants. Such deviations require timely action.

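### Minor, cheap improvement: the primary ANCOVA could also adjust for Japanese origin, a baseline factor the plan recruits to and groups PK by; the gain is small and may be nil

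*Combined protocol and SAP*

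**What the plan says.** Section 9.4.6 defines the primary model as an ANCOVA on natural-log Cmax and AUC0-inf, "including treatment group as fixed effect and with gender as factor and body weight at baseline as continuous covariate". Japanese origin is not in it.

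Elsewhere the protocol treats origin as relevant to PK. Section 9.2 states that "at least 10% (33 participants, 11 per group) participants of Japanese origin are planned to be enrolled". Section 9.4.5 states that "A subgroup analysis of PK parameters by gender and Japanese, non-Japanese ≤80 kg, and non-Japanese >80 kg will also be performed". It also says that "PK parameters will also be summarized by treatment and randomization strata", but the text available for this review does not define those strata.

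Section 9.4.6 adds that "the PK similarity analysis using PK parameters adjusted by protein content will be performed as a sensitivity analysis". It leaves similarity analyses by stratum as optional and exploratory. Section 9.4 defers detail: "A detailed Statistical Analysis Plan (SAP) will be developed and finalized before database lock".

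**The concern.** The plan singles out three baseline characteristics when it groups PK: gender, weight and Japanese origin. The primary model adjusts for the first two only. Any exposure difference by origin that weight and gender do not explain stays in the residual variance and widens the primary 90% CIs. Subgroup summaries do not remove it, because they do not enter the primary model.

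Similarity requires six CIs (three comparisons, two endpoints) to lie inside 80% to 125%, and the stated overall power is 80.5%. Lost precision therefore counts six times. What is at stake is precision only.

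**Working it through.** **Inputs from Section 9.2.** CV 37.7% (Cmax) and 35.0% (AUC0-inf); true GMR 0.95; 101 evaluable per group; 90% CI; margins 80% to 125%; 33 Japanese participants of 336, so p = 33/336 = 0.0982 and p(1 − p) = 0.0886.

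**Input not in the documents.** The residual log-difference d between Japanese and non-Japanese participants after weight and gender. Assumed range 0 to 0.2; d = 0.2 is an exposure ratio of exp(0.2) = 1.22.

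**1. Reproduce the plan's power.** Log variance is ln(1 + CV²): ln(1 + 0.377²) = 0.1329 for Cmax and ln(1 + 0.35²) = 0.1156 for AUC0-inf. The current model has five parameters (three arms, gender, weight), so residual df = 303 − 5 = 298. Two one-sided 5% tests give power of 95.5% (Cmax) and 97.4% (AUC0-inf), as stated. From the rounded figures, (0.955 × 0.974)³ = 80.5%, as stated. From unrounded figures it is 80.4%, which is the baseline below.

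**2. Add origin, balanced across arms.** The variance removed is p(1 − p)d²: 0, 0.00089 and 0.00354 at d = 0, 0.1 and 0.2. Residual df falls from 298 to 297, and the t quantile moves from 1.64998 to 1.65000, about 0.001% of CI width. At d = 0.2 the Cmax log half-width falls from 0.0846 to 0.0835. CI width falls by 0.3% to 0.4% at d = 0.1, and by 1.3% (Cmax) to 1.5% (AUC0-inf) at d = 0.2.

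**3. Add origin, with balance left to chance.** The variance of an adjusted contrast is then multiplied by 1 + (n/2)(pᵢ − pⱼ)²/W. Here n = 101, pᵢ and pⱼ are the Japanese proportions in the two arms, and W is the within-arm sum of squares of the origin indicator. With E(pᵢ − pⱼ)² ≈ 2p(1 − p)/n and W ≈ 3np(1 − p), this is about 1 + 1/(3n) = 1 + 1/303 = 1.0033. Simulated random allocation of 30 Japanese participants (33 × 0.9 ≈ 30) among 303 gives 1.0034. The cost is about 0.17% of CI width. Break-even is where p(1 − p)d²/σ² = 0.0033. For Cmax, d = √(0.1329 × 0.0033/0.0886) = 0.070; for AUC0-inf, with 0.1156 in place of 0.1329, d = 0.066.

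**4. Overall power by the plan's product rule, (Cmax × AUC0-inf)³.**

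| Assumed d | Without term | With term, balanced | With term, chance balance |
|---|---|---|---|
| 0 | 80.4% | 80.4% | 80.2% |
| 0.1 | 80.4% | 80.9% | 80.7% |
| 0.2 | 80.4% | 82.3% | 82.1% |

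**5. Sensitivity, balanced case.**
- The plan's power takes no credit for weight and gender. If they explain an assumed 20% of log variance, overall power is 92.1% without the term and 92.1%, 92.4% and 93.3% with it.
- The product rule treats the six tests as independent. A three-arm simulation with shared arms (AVT05 at 0.95 of both references, references equal, Cmax/AUC correlation 0 and 0.8) gives 87.2% and 89.7% without the term, and 88.4% and 90.8% at d = 0.2.

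**The case against.** The strongest reply is that a recruitment target and subgroup summaries do not oblige a model term. The plan already prespecifies a valid model with two baseline covariates. Leaving out a factor held by about 10% of participants is a defensible parsimonious choice, particularly with weight already included. Section 9.4.5 splits only the non-Japanese group at 80 kg, so origin and weight are intertwined there. No origin effect is given anywhere, so the benefit is assumed. All of this stands, and it limits the point to an optional improvement.

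A reader might infer that the term costs nothing. That holds, to within one residual df, only if origin is balanced across arms. The target of 11 per group suggests balance, but does not establish it. Under chance allocation, d below about 0.07 gives a slight net loss.

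A reader might also infer that the model fails to match the randomization. The supplied text does not include the randomization section and does not say that origin is a stratum, so the point does not rest on this. If origin is a stratum, matching the model to the design would be a further reason to add it.

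The change would also touch the primary model late. Section 8.9 reports that "As of Protocol Version 4.0, the analysis of the samples collected for the ex-vivo pharmacodynamic substudy will not be performed", so samples had already been collected by then. That makes timing a condition of the change; it does not rule the change out while the data are blinded.

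**Conclusion.** The point holds as a minor, cheap improvement. It would be wrong to read the omission as bias, inflated type I error or a faulty sample size: the GMR and test are valid without the term, and the stated power reproduces. Omission is at most mildly conservative.

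On the plan's own product rule, the effect of adding the term runs from a loss of 0.2 points (d = 0, chance balance) to a gain of 1.9 points (d = 0.2, balanced). The gain shrinks if weight and gender explain part of the variance, and it may be nil if they absorb the origin difference.

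This rests on the assumed range for d, on recruitment at the minimum of 33, and on the Section 9.2 CVs already including the variance due to origin. If they do not, omitting the term adds variance and the direction is the same. The full SAP text was not available, so it cannot be said that the final SAP lacks the term.

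**What to change.** First check whether the detailed SAP already includes origin. If it does not, and the SAP is still open and the data blinded, prespecify Japanese origin (yes/no, as defined for enrolment) as an additional factor in the ANCOVA for ln(Cmax) and ln(AUC0-inf). Keep treatment, gender and continuous baseline weight, and use the same model for the protein-adjusted sensitivity analysis. If the data have been unblinded, leave the primary model as it is.

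The cost is one model term in the SAP, one residual df (plus about 0.17% of CI width if origin is not balanced by design), and a matching edit to Section 9.4.6. Section 10.1 governs that edit: "No changes (amendments) to the protocol may be implemented without prior approval from the Sponsor and the appropriate IRB/IEC", apart from the exceptions it lists. The sample size stays at 336. No new data are needed, because the Section 9.4.5 subgroup analysis already requires origin to be recorded.

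### Section 9.2 powers all three unadjusted comparisons at one true GMR of 95% without reconciling that with the protein concentrations in Section 9.4.6; if content-adjusted exposure is equal, AVT05 vs EU has about 77% (Cmax) and 82% (AUC0-inf) power

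*Combined protocol and SAP*

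**What the plan says.** **Product difference.** Protocol Section 9.4.6 states: "Differences in drug protein concentration have been identified between AVT05 (101.0 mg/mL), US-licensed Simponi (94.7 mg/mL), and EU-approved Simponi (91.4 mg/mL"). It responds that "the PK similarity analysis using PK parameters adjusted by protein content will be performed as a sensitivity analysis", with further detail left to the SAP. Section 9.4.5 also plans listings and summaries of the adjusted parameters.

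**Primary test.** Section 9.4.6 uses an ANCOVA on log Cmax and log AUC0-inf, "including treatment group as fixed effect and with gender as factor and body weight at baseline as continuous covariate". No term represents protein content. Similarity requires the 90% CIs for both parameters to "lie entirely within the prespecified margins of 80% and 125"%, in all three pairs (Section 9.2).

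**Power.** Section 9.2 states: "Assuming a true GMR of 95%, 101 evaluable participants per treatment group will provide a power of 95.5% for each individual comparison" of Cmax. The matching figure for AUC0-inf is 97.4%, and overall study power is given as 80.5%. The assumed CVs are 37.7% (Cmax) and 35.0% (AUC0-inf). The section does not mention protein content, nor whether its 95% is the ratio before or after content adjustment.

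**The concern.** The unadjusted GMR is the product of two things: the ratio of protein delivered and the ratio of exposure per unit of protein. The plan gives numbers for the first in Section 9.4.6 and then plans power in Section 9.2 as if there were one common ratio for every pair. For AVT05 vs EU, the content ratio alone is twice as far from unity on the log scale as the planning value (0.100 against 0.051). It takes up about 45% of the distance to the upper margin (0.100 of 0.223).

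One failed comparison fails the whole similarity claim, so the pair with the largest content difference carries the most risk. A reader of Section 9.2 would take every pair to have at least 95.5% power per endpoint, and would not see that this depends on how the 95% relates to protein content.

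**Working it through.** **Inputs.** Section 9.2: n = 101 evaluable per arm; CV 37.7% (Cmax) and 35.0% (AUC0-inf); 90% CI within 0.80-1.25; true GMR 0.95. Section 9.4.6: 101.0, 94.7 and 91.4 mg/mL. Assumptions not in those sections: equal injected volume, and exposure proportional to protein content.

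**Formula.** Log-scale SD s = √ln(1+CV²); SE = s√(2/n); t = 1.653 (95th percentile, 200 df). For true ratio θ,

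power ≈ Φ[(ln 1.25 − ln θ)/SE − t] − Φ[(ln 0.80 − ln θ)/SE + t],

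and the exact value averages this over the distribution of the variance estimate.

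- Cmax: s = 0.3645, SE = 0.0513
- AUC0-inf: s = 0.3399, SE = 0.0478

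**Step 1: reproduce the plan (θ = 0.95, ln θ = −0.0513).** Distance to the nearer margin: 0.2231 − 0.0513 = 0.1718.

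- Cmax: 0.1718/0.0513 − 1.653 = 1.70, power 95.5% (stated 95.5%)
- AUC0-inf: 0.1718/0.0478 − 1.653 = 1.94, power 97.35% exact (stated 97.4%)
- Overall, as six independent tests: (0.955 × 0.974)³ = 80.5% (stated 80.5%)

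**Step 2: content-implied ratios.** 101.0/94.7 = 1.067 (AVT05/US); 101.0/91.4 = 1.105 (AVT05/EU); 91.4/94.7 = 0.965 (EU/US).

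**Step 3: power if content is the only difference.** For AVT05/EU, the distance to the margin is 0.2231 − 0.0999 = 0.1232.

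- Cmax: 0.1232/0.0513 − 1.653 = 0.75, power 77.3%
- AUC0-inf: 0.1232/0.0478 − 1.653 = 0.92, power 82.2%

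| Pair | Unadjusted GMR | Cmax | AUC0-inf |
|---|---|---|---|
| AVT05/EU | 1.105 | 77.3% | 82.2% |
| AVT05/US | 1.067 | 92.5% | 95.2% |
| EU/US | 0.965 | 97.7% | 98.8% |

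**Step 4: overall power in the same case.** Simulation with shared arms gives about 59% with uncorrelated endpoints and about 68% with endpoint correlation 0.8 (the correlation is an assumption). The plan's own multiplication would give (0.773 × 0.822) × (0.925 × 0.952) × (0.977 × 0.988) ≈ 54%. For a like-for-like reference, the same simulation with AVT05 at 0.95 of both references and no content difference gives 87% with uncorrelated endpoints.

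**Step 5: dependence on the content-adjusted ratio, AVT05/EU.**

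| Content-adjusted ratio | Unadjusted GMR | Cmax | AUC0-inf |
|---|---|---|---|
| 0.95 | 1.050 | 96.0% | 97.7% |
| 1.00 | 1.105 | 77.3% | 82.2% |
| 1.05 | 1.160 | 42% | 46% |
| 1/0.95 | 1.163 | 40.3% | 44.2% |

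The stated power needs an unadjusted ratio between 0.95 and 1/0.95 = 1.053. For AVT05/EU that is a content-adjusted ratio between 0.95/1.105 = 0.860 and 1.053/1.105 = 0.953. With AVT05 at a content-adjusted 0.95 against both references, and EU/US differing by content only, overall power is about 90-92%. At 1/0.95 it is about 13% with uncorrelated endpoints.

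**Step 6: covariate gain.** If weight and gender explain 20-30% of variance (an assumption; Section 9.2 gives no figure), AVT05/EU power at 1.105 is about 85-89% (Cmax) and 89-92% (AUC0-inf).

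**The case against.** A reader might infer that AVT05 vs EU simply lacks its stated power. The documents do not support that. Section 9.2 is worded as a conditional statement, and its figures are correct for the ratio it names. If that ratio is content-adjusted, AVT05/EU power is slightly above what is stated. The shortfall needs equal injected volume, exposure proportional to content, and a content-adjusted ratio above about 0.953. Section 9.4.6 gives one concentration per product with no batch or assay precision. This objection stands, and the point is limited accordingly.

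A reader might also infer that the plan overlooks the difference, so that a failed unadjusted comparison could not be explained. That is not supported either: Section 9.4.6 discloses the figures and prespecifies the adjusted similarity analysis. Adjusted and unadjusted results will both be available, so asking for the two side by side, or for the expected ratios in advance, would add almost nothing.

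Nor does it matter that 0.95 lies on the other side of unity from 1.067 and 1.105. The margins are symmetric on the log scale, so only distance counts.

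Covariate adjustment would recover part of the loss, but at 20-30% of variance explained the AVT05/EU figures remain below those stated. Finally, Section 8.9 describes substudy samples as already collected, so restating power changes no test or estimate. That limits the value of the change to a fair account of the risk. It does not remove the mismatch between Sections 9.2 and 9.4.6.

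**Conclusion.** The point holds in conditional form. Section 9.2's power is not reconciled with the protein concentrations in Section 9.4.6, and the plan does not say which ratio its 95% describes. Under equal injected volume, proportional exposure and equal content-adjusted exposure, AVT05/EU power is 18 points (Cmax) and 15 points (AUC0-inf) below the stated values, before any covariate gain. AVT05/US falls slightly short and EU/US gains.

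Equal content-adjusted exposure is a natural reference case for a proposed biosimilar, and it lies outside the 0.860-0.953 range in which the AVT05/EU figures hold. The reading under which nothing is lost applies to AVT05/EU. If the same content-adjusted 0.95 were applied to EU/US, its unadjusted ratio would be 0.95 × 0.965 = 0.917, with power of about 84% and 88%. One common planning ratio therefore cannot stand in for all three pairs.

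None of this shows that the primary criterion is invalid or the sample size wrong.

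**What to change.** In Section 9.2:

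1. State whether the true GMR of 95% is content-adjusted or unadjusted.
2. Restate power for the unadjusted primary test, per pair and overall, at the content-implied GMRs (1.067 AVT05/US, 1.105 AVT05/EU, 0.965 EU/US), naming the assumptions on injected volume and proportionality.
3. Give a range for content-adjusted ratios of 0.95 to 1.05. If credit is taken for weight and gender, state the variance reduction assumed.

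The primary criterion, the sample size and the protein-adjusted sensitivity analysis stay as they are. The cost is a short power re-run and some wording. The downside is a less favourable stated power for AVT05 vs EU. No participants or procedures are added.
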